9.3 HANDLING OF MISSING DATA

In general, missing values will not be replaced, and observed values will be used for analyses unless specified in the sections below.

For the calculation of duration of SBS disease history, if there are any partial dates of SBS disease history, the first day and/or month of the year will be assumed for a missing day and/or month for the purpose of duration calculation based on the worst case scenario approach.

For medication or therapeutic interventions with imprecise/partial date(s), the first day/month of the year will be assumed for unknown day/month of the start date, and the last day/month of the

year will be assumed for unknown day/month of the stop date to categorize medications or therapeutic interventions as concomitant for the worst case scenario.

For events with imprecise/partial date(s), unless the start or end date of the known month or year is before the date of the first trial treatment, all events will be deemed as treatment-emergent adverse events (TEAEs) as opposed to pre-existing AEs.

For analyses of safety, missing data about AE relationship to trial treatment, intensity, seriousness, and outcome will be assumed to be 'related to the trial treatment', 'severe', 'serious', and 'not recovered/not resolved', respectively, based on the worst case scenario.

For analyses of efficacy, weekly PS data from diary may be missing in case of PS being 'weaned off'. In this case, missing weekly PS diary data (e.g. volume, frequency, total time of infusion etc.) will be imputed to 0 for analyses based on 'weaned off' information according to the PS prescription eCRF. Once 'weaned off' is recorded in eCRF at a visit, sites are not asked to repeat this data in the next visit. Hence, for analysis, 'weaned off' data will be carried forward to the next analysis timepoint(s) where applicable based on subjects' visit information until indicated otherwise (i.e. no longer reported as 'weaned off').

9.4 SUBJECT DISPOSITION

Number of subjects who were screened and screen-failures (along with reasons) will be summarized for all screened subjects. The percentages will be calculated based on the total number of subjects screened.

This table will also document the number and percentages of subjects enrolled, enrolled but not treated, in the SAS, and in the FAS. The percentages will be calculated based on the number of subjects screened. The enrolled subjects will be identified as subjects who signed the informed consent form (ICF) and have met all eligibility criteria. The number (%) of subjects screened and enrolled will be also summarized by country.

The number (%) of subjects who completed the trial treatment and prematurely discontinued from trial treatment will be tabulated, along with reasons for discontinuation. The number (%) of subjects who entered and did not enter 4-week safety follow-up will be presented, along with reasons for not entering follow-up. The 4-week safety follow-up completion status will be summarized with counts and percentages, along with the reason for not completing for subjects who have not completed the safety follow-up. The number (%) of subjects continuing with trial visits after withdrawal and subjects who agreed to provide PS administration details to the investigator will also be tabulated in the same table. For such subjects, the extended follow-up (observation) completion status will also be summarized with counts and percentages, along with the reason for not completing trial visits or PS data collection after permanent withdrawal of trial treatment.

The above tabulations will be produced for the SAS and FAS separately.

All disposition data will be listed.

A listing of eligibility and enrollment will be prepared for all screened subjects. A separate listing will be prepared to document subjects excluded from efficacy analysis.

9.5 PROTOCOL DEVIATIONS

Deviations will be collected by the clinical team during the trial conduct and reviewed by the sponsor as outlined in the most current Protocol Deviations Management Plan. The deviations will be classified as major or minor.

Protocol deviations will be tabulated for the SAS. Summaries will include number and

percentage of subjects with at least one major deviation, with at least one minor deviation, and at least one major deviation of each category.

A separate summary of protocol deviations related to COVID-19 will be presented for the SAS.

A listing of all protocol deviations will be produced.

9.6 SUBJECT CHARACTERISTICS

9.6.1 BASELINE AND DEMOGRAPHIC CHARACTERISTICS

Summary tables will include age (in years), sex (including child-bearing potential and reason, if applicable e.g., surgically sterile, post-menopausal, other), race, ethnicity, and country. Weight (kg) and height (cm) will also be tabulated together with body mass index (BMI) (kg/m²). The BMI will be calculated using weight in kg, divided by height in m².

Listings of all baseline and demographic characteristics will be produced.

9.6.2 MEDICAL AND SURGICAL HISTORY

Medical and surgical history will be coded using the Medical Dictionary for Regulatory Activities (MedDRA; version 24.0 or higher). The number and percentage of subjects having at least one medical and/or surgical history record will be presented, along with summaries by System Organ Class (SOC) and preferred term (PT).

All medical and surgical history data collected in the eCRF will be listed.

A summary of SBS disease history will be presented, and this will include the cause of SBS, time from SBS diagnosis, time from PS initiation, length of remnant small bowel (cm), length of remnant colon in percentage (%) according to Cummings classification, time from major intestinal surgery which led to SBS, time from last continuity surgery, and whether ileocecal valve has been preserved. The durations will be derived as follows:

- Time from SBS diagnosis (months) = (date of ICF signed – date of SBS diagnosis +1)/30.4375. Refer to Section 9.3 for handling of the imprecise date of SBS diagnosis.
- Time from PS initiation (months) = (date of ICF signed – date of PS initiation +1)/30.4375. Refer to Section 9.3 for handling of the imprecise date of PS initiation.
- Time from major intestinal surgery which led to SBS (months) = (date of ICF signed – date of major intestinal surgery which led to SBS +1)/30.4375. Refer to Section 9.3 for handling of the imprecise date of major intestinal surgery which led to SBS.
- Time from last continuity surgery (months) = (date of ICF signed – date of last continuity surgery +1)/30.4375. Refer to Section 9.3 for handling of the imprecise date of last continuity surgery.

All SBS disease and gastrointestinal (GI) health history data will also be listed.

9.6.3 PRIOR AND CONCOMITANT MEDICATION AND INTERVENTIONS

All medication records will be categorized as either prior or concomitant medications for analyses. Concomitant medications are any ongoing medications at the time of the first trial treatment or any medications started on or after the date of the first trial treatment. Prior medications are any medications that ended prior to the date of the first trial treatment.

Prior and concomitant medications will be coded by World Health Organization Drug Dictionary (WHODD; version March 2021 Format B3 or higher) and summarized in separate tables by

Anatomical Therapeutic Chemical (ATC) classification 2, ATC classification 4, and PT.

Moreover, there will be a separate summary for concomitant antibiotic and non-antibiotic medications. The antibiotics will be identified by ATC codes starting with J01 or J04.

A subject data listing will be prepared to document all medications, and there will be a flag to identify prior vs. concomitant medications.

Similarly, there will be a subject data listing to document all therapeutic interventions reported.

9.7 EFFICACY ENDPOINTS AND ANALYSIS

In addition to the efficacy analyses defined below, for all continuous efficacy endpoints for the protocol defined analysis timepoints, mean change from baseline to the respective analysis timepoint will be presented with a p -value based on the paired t-test and 95% confidence interval (CI) for the mean change from baseline based on t-distribution. The 95% confidence interval (CI) for the mean change from baseline will be done for both absolute and relative change from baseline. Due to the relatively small sample size, one-sample (paired) Hodges-Lehmann median estimator for non-parametric estimate of change from baseline to the respective analysis timepoint, will be computed with the corresponding 95% CI.

Subject data listings will be prepared to document efficacy data, such as results from MB parameters, wet weight during the MB period, and DEXA scan. This will be supplemented by listings based on data from the MB period summary, including hospital admission information and drinking menu.

All data from the PS diary or PS infusion will also be listed to document efficacy data. This will be supplemented by listings using data from PS prescription, PS evening diary, urine sample for sodium analysis, change in eating/appetite, drinking diary, stool assessment, Bristol stool form scale diary, and stool frequency diary.

There will be separate subject data listings for PRO data from questionnaires, such as the [REDACTED], SBS-IF-TI-QOL, SBS-IF-CIC-QOL, Patient Global Impression of Severity (PGI-S), PGIC, PGI-TS, PGI-SPS, and PGI-PSI.

9.7.1 ANALYSIS OF PRIMARY ENDPOINT

There is no primary efficacy endpoint for this study.

9.7.2 ANALYSIS OF SECONDARY ENDPOINTS

9.7.2.1 ANALYSIS OF SECONDARY ENDPOINTS RELATED TO PS VOLUME

Subject diary data will be used to obtain PS volume information for analyses. Subjects are to complete diary prior to a scheduled visit. If a subject's e-diary data is not available, PS data recorded at the site will be used for analyses. If a subject has issues/difficulties using the e-diary, PS volume data will be captured in the paper diary and will be entered into the electronic data capture (EDC) system at a trial visit.

The relative as well as absolute change in actual weekly PS volume from baseline to every 4 weeks until Week 52 will be summarized by descriptive statistics. p -values and Hodges-Lehmann median estimator along with 95% CI will be produced for Week 24 and Week 52 as defined in the introduction of Section 9.7. The sum of daily PS volume (including extra fluids) from weekly PS diary data recorded for the corresponding analysis timepoint will be used for analysis.

The proportion (%) of subjects who have achieved a reduction of at least 1 day per week of PS from baseline at every 4 weeks until Week 52 will be produced. Subjects will be considered to

have a reduction of at least one day per week of PS from baseline (incl. extra fluids) if the number of days with PS from weekly PS diary data recorded for the corresponding analysis timepoint is smaller compared to the number of days with PS from weekly PS diary data for the baseline.

In addition, the proportion (%) of clinical responders (20% reduction of PS volume from baseline) at every 4 weeks until Week 52 will be produced. Subjects will be considered to be a clinical responder if the relative change from baseline in weekly PS volume is $\leq -20\%$ for the corresponding visit.

For above analyses, missing weekly PS data from diary (e.g. volume, frequency, etc) will be imputed to 0 in case of PS being weaned off (Refer to Section 9.3.).

Moreover, the proportion (%) of subjects with enteral autonomy at every 4 weeks until Week 52 will be produced using eCRF data. Once 'weaned off' is recorded in eCRF at a visit, sites are not asked to repeat this data in the next visit. Hence, for analysis, 'weaned off' data will be carried forward to the next analysis timepoint(s) where applicable based on subjects' visit information until indicated otherwise (i.e. no longer reported as 'weaned off') and enteral autonomy will be identified when there are at least two consecutive wean off records for analysis timepoints (after considering carried forward wean-off records) except for Week 52. For Week 52, enteral autonomy will be identified by 'weaned off' data reported at Week 52 since there is no subsequent/further analysis timepoint.

For PS compliance measure, the percent change in actual weekly PS volume from the prescribed weekly PS volume and the difference in actual days per week of PS from prescribed days per week of PS will be assessed for each post-baseline timepoint as well as for overall using the average per subject. The percent change in actual weekly PS volume from the prescribed weekly PS volume is calculated as $(\text{actual weekly PS volume} - \text{prescribed weekly PS volume}) \times 100$, divided by prescribed weekly PS volume for the corresponding timepoint. The difference in actual days per week of PS from prescribed days per week of PS (day) is calculated as actual days per week of PS minus prescribed days per week of PS.

The energy reduction in the PN from baseline at every 4 weeks until Week 52 will be assessed by descriptive statistics of the absolute and relative change in the total energy prescription data from baseline to analysis timepoints. *p*-values and Hodges-Lehmann median estimator along with 95% CI will be produced for Week 24 and Week 52 as defined in the introduction of Section 9.7. If it is reported that PS is weaned off at the given analysis timepoint, the total energy prescription data will be considered as 0 for analysis.

9.7.2.2 ANALYSIS OF SECONDARY ENDPOINTS RELATED TO NUTRITIONAL, FLUID (WET WEIGHT) AND ELECTROLYTE ABSORPTION

The absolute change in absorption of energy, over MB periods from baseline to Week 48 will be summarized by descriptive statistics.

The absorption will be defined as dietary intake minus output from fecal excretion over a 72-hour MB period at a given analysis timepoint. Hence, the absorption of energy will be calculated as energy intake minus energy output data (as collected on MB Results eCRF). Since dietary intake and fecal excretion are to be measured daily, i.e. up to 3 measurements may contribute to absorption calculations, the average over all available daily absorption measurements over the 72-hour period will be used for analysis. In other words, absorption data will be derived by average of all available intake minus average of all available excretion, regardless of whether there is a case in which either energy intake or energy output data are missing in a daily measurement.

Similar derivations will be applied for absorption of each of the other MB parameters, such as macronutrients (fat, carbohydrate, nitrogen, and protein).

Similarly, the wet weight absorption will be calculated as average of all wet weight input (oral solid + drinks) minus average of all wet weight output (only using feces) under assumption of 1mL = 1g for oral fluids.

Descriptive statistics will be produced for analyses of the following endpoints using absolute and relative change from baseline:

- Relative change in absorption of energy and wet weight over the MB period from baseline to Week 48.
- Absolute change in absorption of energy and wet weight over the MB period from baseline to Week 4 (See above for the derivation of absorption of energy).
- Change in absorption of macronutrients (fat, carbohydrate, and protein) over the MB period from baseline to Week 4 and to Week 48 (See above for the derivation of absorption of macronutrients).
- Change in urinary electrolytes (calcium, magnesium, sodium, potassium, urea, and creatinine) over the MB periods from baseline to Week 4 and Week 48. Since urinary electrolytes data are expected to be measured over the 72-hour MB period, the average of all available results will be used for analyses for each MB parameter at a given analysis timepoint.
- Change in urine volume over the MB periods from baseline to Week 4 and Week 48. This analysis will be based on average daily urine volume data derived as per Balance Period Calculations eCRF since the average daily urine volume should be calculated based on investigator's decision on which 48 hours of the 72 hour metabolic balance study collection to be used.

p-values and Hodges-Lehmann median estimator along with 95% CI will be produced for absolute and relative change from baseline where applicable as defined in the introduction of Section 9.7 for the above analysis timepoints. If a measurement of absorption yields a negative value, such a measurement result will be regarded as invalid and treated as non-evaluable for the relative change analysis. In the analysis dataset, such cases will not be flagged as analysis records since it is considered non-evaluable for the relative change analysis.

The following figures will be provided for energy absorption:

- Line graph using individual observations by timepoint
- Line graph using individual relative change from baseline by timepoint
- Cumulative distribution of change from baseline
- Change from baseline – mean (95%CI) by timepoint
- Relative change from baseline (%) – mean (95%CI) by timepoint

Figures will be repeated for other MB parameters, absorption of wet weight, fat, carbohydrate, and protein.

In addition, the absolute and relative change from baseline in average daily urine volume (derived as per Balance Period Calculations eCRF) will be also summarized for other timepoints. The number of subjects with an increase or decrease from baseline of more than 10% will be tabulated by analysis visit up to Week 52.

Furthermore, the change from baseline in urine sodium will be summarized by descriptive statistics for scheduled time points.

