5.1.3.1 Oral Fluid Intake

The oral liquid intake should be kept constant during the balance studies ensuring that potential changes in any output measurements are not caused by changes in liquid intake. Therefore, the subject's individual oral fluid intake ("drinking menu") will be defined at Screening and confirmed on Day 1 of the baseline metabolic balance study based on the subject's usual oral fluid intake (volume).

Solid oral food intake can be varied according to the subject's own choice.

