7.4 Efficacy analysis

For all continuous efficacy endpoints mean change from baseline to end of treatment will be presented with simple 95% confidence interval and a t-test of no change from baseline. This will be done both for absolute and relative change. Due to the relatively small sample size, a non-parametric estimate of the change from baseline to end of treatment for each endpoint will be derived using the one-sample Hodges-Lehmann median estimator with corresponding 95% confidence interval.

As some of the continuous endpoints can be close to or below zero at baseline (e.g., absorption of energy), the relative change of such endpoints should be interpreted with great caution as the analysis can lead to meaningless results.

Responder endpoints will be tabulated with number of subjects and percentages of subject in FAS.

Other categorical endpoints will be tabulated with number of subjects and percentages of observed subjects. For ordinal endpoints change from baseline will also be calculated and tabulated.

For endpoints related to nutritional status and nutritional absorption sensitivity analyses will be made excluding subjects missing more than 20% of the planned

injections prior to the time of analysis. Hence the number of injections leading to exclusion will be one at Week 4, six at Week 24, and 11 at Week 52.

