- Relative change from baseline = $100 * (X_i - X_0) / X_0$

Where X_i = observed/assessed value at a given analysis timepoint, whereas X_0 = observed/assessed value at baseline.

All analyses will be performed using [REDACTED]

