9.7.3 ANALYSIS OF EXPLORATORY EFFICACY ENDPOINTS

9.7.3.1 ANALYSIS OF EXPLORATORY ENDPOINTS RELATED TO NUTRITIONAL STATUS

The following exploratory endpoints related to nutritional status will be analyzed by descriptive statistics using absolute and relative change from baseline:

- Changes from baseline in lean body mass, bone mineral content and fat mass by DEXA scan from baseline to Week 4, Week 24, and Week 48
- Change in body weight from baseline to Week 4, Week 24, and Week 48
- Change in dietary intake of wet weight (oral solid food, oral fluid), energy, macronutrients (fat, carbohydrate, nitrogen, and protein), and electrolytes (sodium, potassium, calcium and magnesium) from baseline to Weeks 4 and 48
- Change in fecal excretion of wet weight (feces), energy, macronutrients (fat, carbohydrate, nitrogen, and protein), and electrolytes (sodium, potassium, calcium and magnesium) from baseline at Weeks 4 and 48

For each MB parameter, it is expected that there will be up to 3 measurements at a given analysis timepoint based on dietary intake and fecal excretion data; hence, the average of all available results over the 72-hour MB period will be used for analysis for each MB parameter at a given analysis timepoint.

p -values and Hodges-Lehmann median estimator along with 95% CI will be produced for change from baseline as defined in the introduction of Section 9.7 for the above specified analysis timepoints.

The body weight will be summarized by descriptive statistics for scheduled visits. If there are multiple body weight results available over MB period, the last available result taken on or prior to the scheduled visit will be used for the corresponding analysis timepoint (Week 4 or Week 48).

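### Energy and macronutrient absorption is analysed only as intake minus fecal output while solid food is free; the readable plan prespecifies no per-subject absorbed fraction

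*SAP*

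**What the plan says.** SAP 9.7.2.2 defines the variable: "The absorption will be defined as dietary intake minus output from fecal excretion over a 72-hour MB period at a given analysis timepoint". For energy this is average daily intake minus average daily fecal output, and macronutrients are handled the same way. SAP 9.1 gives the relative form as "Relative change from baseline = $100 * (X_i - X_0) / X_0", where X is the absorbed amount itself. The figures in 9.7.2.2 and the sensitivity analyses in 9.7.4 use the same variable.

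On intake, Protocol 5.1.3.1 says of fluids that "The oral liquid intake should be kept constant during the balance studies", so that changes in output are not produced by changes in drinking. For solids it says "Solid oral food intake can be varied according to" the subject's wishes. Protocol 2.2.2 encourages investigators to increase enteral nutrition where suitable. Protocol 5.1.3.2 holds parenteral support (PS) at the baseline programme for the first two balance periods but not for Week 48. All subjects receive apraglutide (Protocol 4.9.1).

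Intake is analysed separately. SAP 9.7.3.1 lists "Change in dietary intake of wet weight (oral solid food, oral fluid), energy, macronutrients (fat, carbohydrate, nitrogen, and protein), and electrolytes" as an exploratory endpoint, with a matching item for fecal excretion. Both get p-values and Hodges-Lehmann intervals at Weeks 4 and 48. SAP 9.7 adds: "Subject data listings will be prepared to document efficacy data, such as results from MB parameters".

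**The concern.** The title question is the effect of apraglutide on intestinal absorption. The amount absorbed is a proper target because it bears on PS energy need. By itself it cannot separate eating more from absorbing a larger share of what is eaten. The protocol controls this problem for fluids by design but has no equivalent for solid food, in design or in analysis.

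The gap matters most at Week 48, after months in which diet may have been increased and PS may have changed. Absolute change in energy absorption to Week 48 was the primary endpoint under protocol version 3 (SAP 7.1) and is a secondary endpoint under version 4.

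The planned relative measure does not help. It moves one-for-one with intake when the absorbed fraction is constant. It is also fragile: Protocol 7.4 warns that "the relative change of such endpoints should be interpreted with great caution as the analysis can lead to meaningless results", and SAP 9.7.2.2 says of a negative absorption value that "such a measurement result will be regarded as invalid and treated as non-evaluable for the relative change analysis".

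Without a planned fraction, readers would have to rebuild it from the listings after the results are known. The concern is weaker for wet weight, because oral fluid follows a fixed drinking menu.

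**Working it through.** The plan gives no sample size, effect size or intake figure for this endpoint, so there is no stated number to reproduce. The check is algebra, an illustration and a simulation.

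**Notation.** I is mean daily intake, O is mean daily fecal output, A = I − O is absorption as the SAP defines it, and f = A / I is the absorbed fraction. Then A = f × I and O = (1 − f) × I.

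**General result, no assumed values.** Hold f constant and let intake go from I0 to I1:

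- Absolute change = f × (I1 − I0)
- Relative change = 100 × (f·I1 − f·I0) / (f·I0) = 100 × (I1 − I0) / I0, the percentage rise in intake
- Change in fraction = 0

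**Illustration.** The inputs are assumptions: baseline I = 2000 kcal/day and f = 60%, so A = 1200 and O = 800.

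| Scenario | I | f | A | Change in A | Change in O | Change in f |
|---|---|---|---|---|---|---|
| Diet alone | 2400 | 60% | 1440 | +240 (+20%) | +160 (+20%) | 0 points |
| Mixed | 2200 | 65.5% | 1440 | +240 (+20%) | −40 (−5%) | +5.5 points |
| Function alone | 2000 | 72% | 1440 | +240 (+20%) | −240 (−30%) | +12 points |

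Both planned absorption measures give the same answer in all three rows.

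**Range for diet alone.** With assumed intake of 1500 to 3000 kcal/day, f of 40% to 80% and an intake rise of 5% to 25%, the apparent gain runs from 1500 × 0.40 × 0.05 = 30 to 3000 × 0.80 × 0.25 = 600 kcal/day.

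**The reverse.** If f rises from 50% to 60% while intake falls by one sixth from 2000, then A goes from 0.50 × 2000 = 1000 to 0.60 × 1666.7 = 1000. A real gain in the fraction shows as no change.

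**Simulation of the planned paired t-test with f unchanged on average.** It used 20,000 runs per setting at n = 9, the number enrolled (2 + 7, SAP 2). Assumed inputs were intake 2000 (SD 500) kcal/day, f = 50% (between-subject SD 10 points, within-subject SD 3 points per period), and an SD of intake change of 10 or 20 percentage points.

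| Mean intake change | Absorbed amount: p < 0.05 in the direction of benefit | Absorbed fraction: same criterion |
|---|---|---|
| 0 | about 2% | 2.3–2.6% |
| +10% | 19% (SD 20) to 46% (SD 10) | 2.5% |
| +20% | 62% (SD 20) to 95% (SD 10) | 2.4–2.5% |

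At +10%, the figures for the absorbed amount are 18–40% for n = 8 and 22–52% for n = 10.

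**The case against.** The strongest reply is that the plan already supplies most of the answer. SAP 9.7.3.1 analyses intake and fecal excretion of energy and macronutrients with intervals, and the fecal column of the illustration separates the three scenarios. At group level, a diet-driven gain could therefore be told from a functional one. That stands, and it is why this is a request for an added analysis and not a claim that the confounding would go unseen. It does not supply the within-subject change in the ratio or its interval, which depends on how intake and output move together in each subject.

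Second, absolute absorption is the protocol's chosen endpoint, and higher intake is an acknowledged part of the treatment course. This also stands. The simulated rates are not false positives for amount absorbed, which does rise in those runs. They are errors only if the result is read as improved gut function.

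Third, the trial is small and exploratory, its primary objective is safety, and no decision hangs on these p-values. That limits the weight of the point but does not remove it.

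Fourth, SAP 2 calls the second interim analysis upcoming, so the first, planned for when the last subject completed Week 4, has probably been run. A fraction added now would not be fully prespecified at Week 4. Week 48, where the concern is greatest, is less affected.

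Finally, the fraction may itself vary with intake. If intake rises 20% from 2000 kcal/day and f falls from 60% to 55%, absorption still rises by 0.55 × 2400 − 1200 = 120 kcal/day. Neither measure is sufficient alone.

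**Conclusion.** The concern holds on the readable text. Energy and macronutrient absorption is analysed only as a difference, and the relative version is not scaled to intake. A larger diet at an unchanged absorbed fraction therefore registers as increased absorption, one-for-one on the relative scale. That result needs no assumption. The kcal/day figures and simulated percentages rest wholly on assumed intakes, fractions and variability, because the documents give none.

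This should be corrected, but it does not invalidate the planned endpoint. Confidence is medium: the Note to File supersedes the SAP where they differ, and its text, the table shells and the redacted endpoints are not available. If any of them already contains an absorbed fraction, the point falls away.

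**What to change.** Add a supportive analysis to SAP 9.7.2.2:

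- Per subject at baseline, Week 4 and Week 48, derive fractional absorption = 100 × (mean intake − mean fecal output) / mean intake, from the 72-hour averages already defined.
- Do this for energy, fat, carbohydrate and protein, and for wet weight for completeness.
- Report the change in percentage points with the t-based and Hodges-Lehmann 95% intervals already planned. Place it beside absolute absorption and the intake and excretion changes, and interpret absolute gains in its light.
- State that negative fractions are kept. Because the denominator is intake, the measure stays defined when absorption is near or below zero.
- Keep absolute absorption as planned and add no success rule.
- Record that the Week 4 fraction was added after the first interim analysis, if that is so.

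The cost is one derived variable from data already on the MB Results eCRF and a few table rows. Since the fraction can depend on intake, both measures should always be shown together.
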